8.3. Rescreening

Individuals who sign the ICF to participate in the study but who do not subsequently meet all the requirements as outlined in the inclusion and exclusion criteria and therefore do not enroll (screen failures) may be rescreened. Such individuals may be allowed to rescreen up to one time.

8.4. Study Withdrawal, Removal, and Replacement of Patients

If a patient discontinues study treatment and is withdrawn from the study for any reason, the study site must immediately notify the medical monitor. The date and the reason for study discontinuation must be recorded on the electronic case report form (eCRF). Patients who complete or discontinue early from the study will be asked to return to the study site within 4 weeks of the last administration of study drug to complete EOT assessments as indicated in the

Schedule of Assessments (Table 4). If the study treatment is permanently discontinued, the patient will remain in the study to be evaluated for safety.

In the event that a patient discontinues prematurely from the study because of a TEAE or serious TEAE assessed as \geq Grade 3 (\geq Grade 2 for the system organ class [SOC] of cardiac disorders) according to Common Terminology Criteria for Adverse Events version 5 (CTCAE v 5), the TEAE or serious TEAE will be followed up until it resolves (returns to normal or Baseline values) or stabilizes, or until it is judged by the Investigator to no longer be clinically significant.

Once a patient is withdrawn from the study, the patient cannot reenter the study.

A patient may voluntarily withdraw or be withdrawn from the study at any time for reasons including, but not limited to, the following:

- unacceptable toxicity or AE
- patient's withdrawal of consent: at any time, a patient's participation in the study may be terminated at his/her request or on the basis of the Investigator's clinical judgment. The reason for patient withdrawal will be noted on the eCRF.
- intercurrent illness: a condition, injury, or disease unrelated to the primary diagnosis that became apparent during treatment and necessitated the patient's termination from the study
- general or specific changes in the patient's condition that renders him/her ineligible for further treatment according to the inclusion/exclusion criteria
- patient fails to adhere to the protocol requirements (eg, drug noncompliance, failure to return for defined number of visits)
- lost to Follow up: the patient stopped coming for visits, and study personnel were unable to contact the patient
- pregnancy, as indicated in Section 12.9.6.

Additionally, the Sponsor may stop the study at any time for safety, regulatory, legal, or other reasons aligned with good clinical practice (GCP). This study may be terminated at the discretion of the Sponsor or any regulatory agency. An Investigator may elect to discontinue or stop the study at his or her study site for any reason, including safety or low enrollment.

8.5. Suspension or Premature Termination of the Clinical Investigation

The sponsor or designee reserves the right to close the study site or terminate the study at any time for any reason at the sole discretion of the sponsor. Study sites will be closed upon study completion. A study site is considered closed when all required documents and study supplies have been collected and a study-site closure visit has been performed.

The Investigator may initiate study-site closure at any time, provided there is reasonable cause and sufficient notice is given in advance of the intended termination.

Reasons for the early closure of a study site by the sponsor or Investigator may include but are not limited to:

For study termination:

• Discontinuation of further development of the study drug

For site termination:

- Failure of the Investigator to comply with the protocol, the requirements of the institutional review board (IRB)/independent ethics committee (IEC) or local health authorities, the sponsor's procedures, or GCP guidelines
- Inadequate or no recruitment (evaluated after a reasonable amount of time) of patients by the Investigator.

If the study is prematurely terminated or suspended, the sponsor shall promptly inform the investigators, the IECs/IRBs, the regulatory authorities, and any contract research organization(s) used in the study of the reason for termination or suspension, as specified by the applicable regulatory requirements. The Investigator shall promptly inform the patient and should assure appropriate patient therapy and/or follow up.

9. TREATMENTS

9.1. Details of Study Treatments and Dosage Schedule

Tablets should be taken in the morning and in the evening approximately every 12 hours. The minimum time interval between 2 consecutive doses is 6 hours. The first dose of the study drug should be taken in the evening of Day 1. Pharmacokinetic (PK) studies have shown no difference whether the product is taken under fasted condition or during a low-fat meal. Intake during a high-fat meal leads to higher blood concentrations, and possibly higher incidence of GI side effects and must, therefore, be avoided. Refer to Table 1 for details about study treatment and dosage schedule.

Table 1. Study Treatment and Dosage Schedule

ARM name:	Orismilast 20 mg BID	Orismilast 30 mg BID	Orismilast 40 mg BID	Placebo							
Name:	Orismilast	Orismilast Orismilast Orismilast									
Type:	ype: Drug										
Dose formulation:	rmulation: 10 mg and 30 mg tablet or matching placebo tablet										
Frequency:	BID (approximately every 12 hours)										
Administered tablets:	2 × 10 mg orismilast tablets BID	1 × 30 mg orismilast tablet and 1 x placebo tablet BID	1 × 10 mg and 1 × 30 mg orismilast tablets BID	2 × placebo tablets BID							
Route:	Oral										
Use:	Experimental Placebo										
Sourcing:	Provided centrally by the Sponsor										
Packaging and labeling:	Investigational medicinal product will be provided in individually labeled wallet cards with blistered tablets. Each card will be labeled as required per country requirement										

Abbreviation: BID, twice daily.

9.2. Measures to Minimize Bias: Study Treatments

9.2.1. Method of Study Treatment Assignment

At the investigational site, each screened patient will be assigned a patient identifier number during Screening that will be used on all patient documentation. The patient identifier number will contain the site number and the patient number and will be assigned in numerical order at the Screening visit based on chronological order of Screening dates (eg, 01-010 for the 10th patient screened at the Site #01).

Randomization will occur prior to first study treatment administration, at the Baseline visit. Patients will be assigned randomly in a 1:1:1:1 ratio to 1 of 3 orismilast dose groups (20 mg, 30 mg, or 40 mg) or placebo.

A randomization list will be used to assign the treatments to each patient. The randomization list will be kept secured with access restricted to only the designated personnel directly responsible for labeling and handling the study drug until the study blind is broken at the end of study (database lock). Further guidance and information can be obtained in the study manual.

9.2.2. Blinding

To facilitate the double blind, the tablets will be packaged in the same type of blister and the active and placebo tablets will have the same appearance (in terms of size, form, weight, and color). One dose consists of 2 identical tablets (a 10 mg or 30 mg orismilast tablet or a matching placebo).

Blinding codes should only be broken in emergency situations for reasons of patient safety. When the blind for a patient has been broken, the reason must be fully documented in the source document and eCRF. Whenever possible, the Investigator should contact the sponsor or its designee before breaking the blind. If the blind is broken, the Investigator should promptly inform the medical monitor. Documentation of breaking the blind should be recorded with the date/time and reason why the blind was broken, and the names of the personnel involved.

The patient for whom the blind has been broken will be discontinued from the study and undergo the early termination procedures. The primary reason for discontinuation (the event or condition which led to the unblinding) will be recorded.

The Interactive Web Response System (IWRS) will be programmed with blind-breaking instructions. In case of an emergency, the Investigator has the sole responsibility for determining if unblinding of a patients' treatment assignment is warranted. Patient safety must always be the first consideration in making such a determination. If the Investigator decides that unblinding is warranted, the Investigator should make every effort to contact the sponsor prior to unblinding a patient's treatment assignment unless this could delay emergency treatment of the patient. If a patient's treatment assignment is unblinded, the sponsor must be notified within 24 hours after breaking the blind. The date and reason that the blind was broken must be recorded in the source documentation and case report form, as applicable.

All patients will be centrally assigned to randomized study treatment using an IWRS. Before the study is initiated, the telephone number and call-in directions for the log in information and directions for the IWRS will be provided to each site.

Study drug will be dispensed at the study visits summarized in the Schedule of Assessments (Table 4). Returned study drug should not be redispensed to the patients.

Sponsor safety staff may unblind the study drug assignment for any patient with an SAE. If the SAE requires that an expedited regulatory report be sent to one or more regulatory agencies, a copy of the report, identifying the patient's study drug assignment, may be sent to investigators in accordance with local regulations and/or sponsor policy.

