7. INVESTIGATIONAL PLAN

7.1. Description of Overall Study Design and Plan

This multicenter, randomized, double-blind, placebo-controlled, parallel-group, Phase 2b doseranging study is designed to assess the efficacy and safety of modified-release orismilast compared with placebo in adult patients with moderate-to-severe plaque-type psoriasis. Efficacy and safety outcomes will be evaluated to select an appropriate orismilast dose for subsequent Phase 3 studies. The study will be conducted in approximately 40 centers in Europe and North America.

After a Screening visit up to 28 days before Baseline, approximately 200 patients will be assigned randomly in a 1:1:1:1 ratio to receive 1 of the 3 orismilast doses (20 mg, 30 mg, or 40 mg) or placebo twice daily (BID) for 16 weeks, with a 4-week Follow-up visit. Administration will begin at Baseline with a dose titration period. The maximum duration of study participation is approximately 24 weeks.

Patients will be seen at the site on Screening, Baseline (Day 1), and Weeks 1, 2, 4, 8, 12, 16 (End-of-Treatment [EOT] visit), and 20 (Follow-up visit, 4 weeks after treatment completion or discontinuation). Visits at Weeks 1 and 2 could be conducted via a telemedicine procedure at Investigator's discretion.

N=50 Orismilast 20 mg BID (2 x 10 mg tablets) N=50 Orismilast 30 mg BID Screening (1 x 30 mg tablet and 1 x placebo tablet*) N=50 Orismilast 40 mg BID (1 x 10 mg tablet and 1 x 30 mg tablet) N=50 Placebo BID (2 x placebo tablets)* **Treatment Period** Follow up Randomization End of Period (16 weeks) Treatment (1:1:1:1)

Figure 1. Study Design

Abbreviation: BID, twice a day

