9.3. Dosage Modification

If a patient experiences a TEAE assessed as ≥Grade 3 (≥Grade 2 for the SOC of Cardiac Disorders) according to CTCAE v 5, the patient should be permanently discontinued from the study drug and not receive additional doses. As a reminder Grade 3 is defined as "Severe or medically significant but not immediately life threatening; hospitalization or prolongation of hospitalization indicated; disabling; limiting self-care activities of daily living (ADL)".

If GI or other AEs considered probably or definitely related to the study drug are reported with a severity not compatible with maintaining the treatment as per protocol during the treatment uptitration and/or during maintenance period, the Investigator might consider decreasing the regimen as described in Section 9.3.1.

If the study drug is permanently discontinued, the patient will remain in the study to be evaluated for safety.

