### 7.4. Visit Windows

If there are multiple planned assessments for any study procedure at a given time point, the latest non-missing value will be used for summarization. Unscheduled assessments will be listed and will be used to flag baseline visit if this is the last non-missing assessment before the first dose of study drug, but unscheduled assessments will not be included in the summarization, unless to be used to avoid missing data at Week 4, 8, 12, 16 and 20.

Visits in RAVE captured as 'Week 16 / EoT and 'Week 20 / Follow-up' will be reassigned to either 'Week 16' or another scheduled post-baseline visit or 'EoT' and 'Week 20' or 'Follow-up' as follows: If a patient completed the study treatment (based on the End-of-Treatment form information), data captured in RAVE as 'Week 16 / EoT', will be presented as 'Week 16' irrespectively of violation of visit window. If a patient discontinued the study treatment, provided that no data are available from a certain scheduled post-baseline visit (Week 4, 8, 12, 16) for a subject, data captured on the 'Week 16 / EoT' visit have the potential to be assigned to a particular scheduled visit in data summaries and analyses, provided the data are collected between 13 days before and 14 days after the planned time point for the scheduled visit, as displayed in table below:

This document is confidential.

Visit (target day)	Visit window (day is date of assessment minus date of first dose)
Week 4 (day 28)	Day 15 to 42
Week 8 (day 56)	Day 43 to 70
Week 12 (day 84)	Day 71 to 98
Week 16 (day 112)	Day 99 to Day 139 *

\* Week 16 uses a broader visit window.

If the 'Week16/EoT' visit falls outside the visit schedule in the trial procedure it will be present as 'EoT'.

If the subject completed study treatment, data captured in RAVE as 'Week 20 / Follow-up' will be presented as 'Week 20' irrespectively of violation of visit window. If the subject did not complete study treatment, data captured in RAVE as 'Week 20 / Follow-up' will be presented as 'Follow-up'.

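### Emergency unblinding removes a patient from the study while stopping drug keeps the patient in for safety, so the 4-week Follow-up safety visit may be lost for a few patients

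*Protocol*

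**What the plan says.** Two rules cover a patient who comes off study drug in an emergency.

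- **Unblinding rule.** Protocol 9.2.2 (Blinding) says: "The patient for whom the blind has been broken will be discontinued from the study and undergo the early termination procedures". SAP 4.4 repeats this in the same words.
- **Stopping-drug rule.** Protocol 9.3 (Dosage Modification) says that after a TEAE of Grade 3 or higher (Grade 2 or higher for cardiac disorders) "the patient should be permanently discontinued from the study drug and not receive additional doses". It then adds: "If the study drug is permanently discontinued, the patient will remain in the study to be evaluated for safety". Protocol 8.4 has the same provision: "If the study treatment is permanently discontinued, the patient will remain in the study to be evaluated for safety".

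Protocol 8.4 also says that patients who complete or leave early "will be asked to return to the study site within 4 weeks of the last administration of study drug to complete EOT assessments", and that "Once a patient is withdrawn from the study, the patient cannot reenter the study". Protocol 7.1 describes Week 20 as the "Follow-up visit, 4 weeks after treatment completion or discontinuation". SAP 7.4 provides for such records: "If the subject did not complete study treatment, data captured in RAVE as" the Week 20 or Follow-up visit are shown under the Follow-up label.

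**The concern.** Codes may be broken only in a safety emergency, so the patients affected have usually just had a serious problem. Many of them will also have to stop drug. For such a patient one rule says leave the study and the other says stay in it. A site that follows the more specific rule, 9.2.2, could reasonably close the patient out at the early termination visit.

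At stake is the scheduled check four weeks after the last dose. Protocol 5.3 names weight loss and major depression as possible class effects to be monitored. Protocol 12.9.2 makes a positive C-SSRS answer, a HADS score of 15 or more, and weight loss above 5% adverse events of special interest. These are found largely by interview, questionnaire or weighing, and the Follow-up visit schedules all three. The safety endpoints in 6.2.2.3 extend over the 4-week Follow-up Period, and SAP 12.1 tabulates AEs that start in it.

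**Working it through.** The plan gives no figure on this point, so there is none to reproduce. The check compares the texts and then counts visits and days.

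**1. Do the two rules overlap?** Yes. A TEAE of Grade 3 or higher triggers the 9.3 stop, and the same emergency can trigger a code break under 9.2.2. A patient removed from the study under 9.2.2 also stops drug for good. Neither rule makes an exception for the other.

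**2. Does any text rank them?** None was found. Protocol 15 lets the SAP supersede the protocol where they differ, but that statement concerns the analysis, and SAP 4.4 only repeats 9.2.2.

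**3. Which visits are assured?** In Protocol Table 4, early termination shares the Week 16 column, and Week 20 Follow-up is a separate column.

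- Patient kept in for safety: EOT/ET + Follow-up = 2 scheduled contacts after stopping drug.
- Patient removed under 9.2.2: ET = 1 assured contact.
- Possible loss: 2 − 1 = 1 visit, or 0 if the site still holds the Follow-up visit because of 7.1.

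**4. What does the lost visit carry?** The safety assessments marked at Week 20 in Table 4 are physical examination, vital signs, weight, AE review, C-SSRS and HADS, which makes 6. ECG and safety laboratory tests are not scheduled at Week 20, so they are not lost.

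**5. How long is the gap?** Days without a scheduled check = 28 − days from last dose to ET visit. Protocol 8.4 allows ET up to 4 weeks after the last dose.

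| ET visit after last dose | Gap |
|---|---|
| 0 days | 28 − 0 = 28 days |
| 14 days | 28 − 14 = 14 days |
| 28 days | 28 − 28 = 0 days |

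TEAEs count up to 7 days after the last dose (Protocol 12.9.1), so at most 28 − 7 = 21 days of the gap lie beyond that window.

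**6. What is still covered?**

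- Protocol 8.4: TEAEs of Grade 3 or higher (Grade 2 or higher cardiac) that lead to leaving the study are followed until they resolve, stabilize or are no longer clinically significant.
- Protocol 12.9.4: SAEs are reported up to 30 days after stopping treatment.
- Protocol 12.9.1: known AEs are followed to resolution or a stable state.
- Table 4: the ET visit itself includes C-SSRS, HADS, weight, vital signs and examination.

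What is left exposed is a new, non-serious finding that arises after the ET visit.

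**7. How many patients?** The documents give no code-break rate. If 0.5% to 2% were unblinded (an assumption), 200 × 0.005 = 1 and 200 × 0.02 = 4, so 1 to 4 patients and at most 1 to 4 visits.

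**8. Is the primary result touched?** No. The endpoint is at Week 16, and SAP 7.4 labels the late visit of a treatment non-completer as Follow-up. Losing that visit removes no Week 16 value.

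**The case against.** The strongest reply is that this is a specific rule beside a general default, which is ordinary drafting. Protocol 8.4 itself expects some patients with severe TEAEs to leave the study and still be followed, so staying in is not absolute. The Follow-up visit in 7.1 depends on stopping treatment and not on study status, and an unblinded patient has stopped treatment. Protocol 12.9.1 collects AEs up to that visit with no exception for unblinded patients. The 8.4 sentence that mentions only EOT assessments also covers completers, who plainly attend Week 20, so it is not a full list of visits. The bar on re-entry does not forbid a safety visit.

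Most of this stands. It makes the loss possible rather than certain, and it shows that the emergency event itself is followed. It does not close the gap, because no sentence says that a patient removed under 9.2.2 attends the Follow-up visit.

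A reader might infer two stronger points that the documents do not support:

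- **That safety follow-up ends at the code break.** The provisions in step 6 of the working show otherwise.
- **That the pregnancy rule in 12.9.6 is a stay-in-study model that 9.2.2 should have matched.** Protocol 8.4 lists pregnancy among the reasons for withdrawal, so it is not a clean comparator.

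**Conclusion.** The point holds as a minor safety-monitoring gap. The two rules give different instructions when both apply, and the text does not say which governs. Per affected patient the loss is 0 or 1 visit with six safety assessments, and the time without a scheduled check is 0 to 28 days. This rests on reading 9.2.2 as governing and on the site then not holding the visit. The number of patients is unknown; 1 to 4 is an illustration from an assumed rate.

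The effect on the tables is also small. SAP 12.7 defines suicidal ideation and behavior by answers during treatment, so a Follow-up C-SSRS would not enter that count. What would be thinner is the monitoring of these patients, the by-visit shift tables and the table of AEs starting in the Follow-up Period.

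A reader might go on to infer a bias in the efficacy results from ratings made after unblinding. That is a separate matter and does not follow from a lost safety visit. Protocol 9.2.2 already has the date and time of unblinding recorded, so such ratings can be identified.

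**What to change.** In Protocol 9.2.2 and SAP 4.4, replace the instruction to discontinue the unblinded patient from the study. State that the patient permanently stops study drug, completes the EOT/ET assessments and stays in the study for safety evaluation through the 4-week Follow-up visit, unless consent is withdrawn. This brings the unblinding rule into line with 8.4, 9.3 and 7.1.

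The cost is one sentence in each document and at most one extra visit for a few patients. Sample size, significance level and the primary analysis do not change.

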9.3. Dosage Modification

If a patient experiences a TEAE assessed as ≥Grade 3 (≥Grade 2 for the SOC of Cardiac Disorders) according to CTCAE v 5, the patient should be permanently discontinued from the study drug and not receive additional doses. As a reminder Grade 3 is defined as "Severe or medically significant but not immediately life threatening; hospitalization or prolongation of hospitalization indicated; disabling; limiting self-care activities of daily living (ADL)".

If GI or other AEs considered probably or definitely related to the study drug are reported with a severity not compatible with maintaining the treatment as per protocol during the treatment uptitration and/or during maintenance period, the Investigator might consider decreasing the regimen as described in Section 9.3.1.

If the study drug is permanently discontinued, the patient will remain in the study to be evaluated for safety.

9.3.1. Titration

Titration of oral apremilast was shown to improve the GI tolerance and overall acceptability of the drug (Zerilli 2015). Similarly, a slow increase in orismilast dose was associated with less GI side effects when compared with a rapid increase. Consistent with this approach, this study will titrate the study treatment dose over a period of maximum 2 weeks (see Table 2).

If tolerability issues arise during the treatment up-titration and/or during maintenance period, the following treatment pauses are allowed only if instructed by the Investigator:

- First day: The Investigator is informed of the tolerability issue; thus, the evening dose can be skipped.
- Second day: Morning dose can be skipped. The patient must take the evening dose.
- Third day: Similar to Day 2, morning dose can be skipped. The patient must take the evening dose.
- Fourth day: BID daily dosing regimen is reintroduced.

The aforementioned treatment pauses do not impact calculation of dosing days and duration of titration is not prolonged. Treatment pauses will be captured in the eCRFs. This titration will not break the blind as all patients will receive 2 of indistinguishable orismilast or placebo tablets BID.

Table 2. Dose Titration Schedule

Arm	Day 1	Da	y 2	Da	у 3	Da	y 4	Da	y 5	Da	y 6	Da	y 7	Da	ıy 8	Da	y 9	Day	y 10	Day	/ 11	Day	y 12	Day	/ 13	Day	14	From I	Day 15
20 mg BID	10	10	10	10	10	10	10	10	20	10	20	10	20	20	20	20	20	20	20	20	20	20	20	20	20	20	20	20	20
30 mg BID	10	10	10	10	20	20	20	20	20	20	30	20	30	20	30	30	30	30	30	30	30	30	30	30	30	30	30	30	30
40 mg BID	10	10	10	10	20	20	20	20	20	20	30	20	30	20	30	30	30	30	30	30	30	30	40	30	40	30	40	40	40
Placebo	Р	Р	Р	Р	Р	Р	Р	Р	Р	Р	Р	Р	Р	Р	Р	Р	Р	Р	Р	Р	P	Р	Р	Р	Р	Р	Р	Р	P

Abbreviation: BID, twice daily

